PET = positron emission tomography; DCE-MRI = dynamic contrast-enhanced magnetic resonance imaging; DVT = deep vein thrombosis; HA = hyaluronan; PD = progressive disease; PEGPEM = PEGPH20 + pembrolizumab; PK = pharmacokinetics; T3 = triiodothyronine; T4 = total thyroxine; TSH = thyroid stimulating hormone; Wk = Week; NSCLC = non-small cell cancer.

Note: Visit window is ± 2 days of the specified times.

- ^a See Section 8.2 for details on individual assessments.
- ^b Subjects should return to the study site for an End of Treatment Visit within approximately 7 days after determination of PD or within 7 days after treatment discontinuation of PEGPH20 and pembrolizumab for other reasons.
- c After the End of Treatment Visit, subjects will enter long-term follow-up during which information on the subject's survival and subsequent anti-cancer therapy will be obtained by the site every 12 weeks. Long term follow-up will continue until the subject dies, is lost to follow-up, or withdraws consent.
- ^d Vital signs will be done pre dose on Day 1, Day 8 and Day 15 of all cycles and End of Treatment Visit. On all other days, vital signs will be collected for clinically significant AEs.
- ^e 12-lead ECG will be done at end of treatment and on an as needed basis when clinically indicated.
- f Tumor assessment scans (CT/MRI of chest, abdomen, pelvis, and other areas of known or newly suspected disease) will be obtained and evaluated locally for response evaluation based on Response Evaluation Criteria in Solid Tumors (RECIST) v 1.1 criteria and irRC at the end of Cycle 2, Cycle 4 and then at the end of every fourth treatment cycle thereafter (i.e., Week 3 of Cycles 2, 4, 8, 12, 16 and beyond). Scans will also be sent to the Central Imaging Vendor (CIV) to be stored for possible central review at a later date, if needed. Scans may be obtained any time on or after Day 15 (of Cycles 2, 4, 8, 12, 16 and every fourth treatment cycle thereafter) to allow enough time for the scan to be reviewed locally prior to the subject's next scheduled dosing visit. For subjects who are withdrawn from the study due to clinical disease progression, a CT/MRI scan should be requested as soon as possible after clinical progression is determined.

 g CT/MRI should only be done if radiologic progressive disease was not documented in the previous CT/MRI scan.

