6.1.3. Study Duration

The study will consist of a Screening period of up to 28 days, a treatment period (21-day cycles), a 30-day post-treatment period (after last dose) for collection of AEs and a long-term follow-up. Subjects will be allowed to continue treatment on study until disease progression (as defined in Section 6.1.4) or unacceptable toxicity. Subjects with asymptomatic disease progression however, will be allowed to continue the study treatment at the Investigator's discretion despite evidence of increasing tumor burden or appearance of new lesions for up to 6 weeks if the subject is clinically stable.

Investigators may also discontinue study treatment if it is no longer in the best interest of the subject. Subjects who discontinue treatment with PEGPH20 and pembrolizumab will be followed every 12 weeks for survival until death, withdrawal of consent, or lost to follow-up.

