7.3. Subject Withdrawal Criteria

7.3.1. Discontinuation of Treatment

The Investigator must guard the subject's welfare and may discontinue study drug treatment at any time when this action appears to be in the subject's best interest. The reason for the subject's withdrawal must be recorded in the subject's electronic case report form (eCRF). Possible reasons for such actions may include, but are not limited to, the following:

- Disease progression (defined in Section 6.1.4).
- AE.
- Any significant protocol violation (e.g., demonstrated lack of treatment compliance, subject starts taking any concomitant anti-cancer therapy).

^{*}Any relevant diseases that are not listed as examples of exclusionary diseases are to be discussed with the Sponsor.

- Withdrawal of consent by an enrolled subject, either for study treatment itself (and subsequent follow-up) or for participation in follow-up.
- Other reasons as determined by the Investigator or Sponsor: a subject may have study treatment discontinued if, in the opinion of the Investigator or Sponsor, it is not in the subject's best interest to continue.
- The subject becomes pregnant (treatment must be discontinued immediately).
- Treatment delay ≥ 21 days.
- Subjects experiencing any TE event that requires full-dose anticoagulation while on study (PEGPH20 will be discontinued; treatment with pembrolizumab may continue as deemed appropriate by the Investigator).
- Gastric adenocarcinoma subjects for whom enoxaparin is discontinued for any reason (PEGPH20 will be discontinued; treatment with pembrolizumab may continue as deemed appropriate by the Investigator).

Subjects who discontinue treatment with PEGPH20 and pembrolizumab should enter long-term follow-up unless they withdraw consent, die, or are lost to follow-up.

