7.3.2. Discontinuation from Study

After discontinuing study treatment (PEGPH20 and pembrolizumab treatment), the subject will enter long-term follow-up for assessment of survival and subsequent anti-cancer therapies (Section 8.1.2.4). Long-term follow-up will continue until the subject discontinues from the study. The reason for the subject's discontinuation from the study should be documented in the subject's eCRF. Possible reasons for study discontinuation include the following:

- Death.
- Withdrawal of consent.
- Lost to follow-up.
- Sponsor termination of the study.
- Other.

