8.1.2.4. Long-Term Follow-Up

After the End of Treatment Visit, all subjects will enter long-term follow-up during which information on the subject's survival status and subsequent anti-cancer therapies (i.e., therapies received, responses) will be obtained by the site once every 12 weeks. Long-term follow-up will continue until the subject dies, is lost to follow-up, or withdraws consent.

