8.3.1.2. Hypersensitivity to PEGPH20

In the event of a hypersensitivity reaction, the PEGPH20 infusion should be stopped and the symptoms should be treated as necessary. Halozyme should be contacted immediately (see study manual for contact information).

At the Investigator's discretion and after discussion with the Sponsor, a re-challenge for the next visit may be done if the reaction is not considered anaphylaxis and is \leq Grade 2. Any subject with anaphylaxis or a \geq Grade 3 hypersensitivity reaction/infusion reaction should be discontinued from the study. In the event of a \leq Grade 2 hypersensitivity/infusion reaction, the Sponsor and Investigator will agree on how subsequent injections will be administered. In general, a re-challenge should be done after pre-medication with a combination of IV diphenhydramine, IV H2 blockers (such as famotidine), and IV dexamethasone. If the hypersensitivity reactions are experienced at the re-challenge, the subject should be discontinued from the study.

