10.7. Pregnancy

Pregnancy itself is not regarded as an AE unless there is suspicion that the study drug may have interfered with the effectiveness of the contraceptive medication. Refer to the pembrolizumab Prescribing Information for the summary of risks in this specific population. Based on its mechanism of action, pembrolizumab can cause fetal harm when administered to a pregnant woman. Women of childbearing potential should therefore use highly effective contraception during treatment with pembrolizumab and refrain from breast feeding for 4 months after the last dose of pembrolizumab. Pregnancy within 120 days of study drug discontinuation in a subject must be reported to the designated safety contact (contact information is provided in the study reference binder) **IMMEDIATELY AND NO LATER THAN 24 HOURS OF**

AWARENESS. Complete the study-specific Pregnancy Report Form with all available information and submit the form with pregnancy test results and any other pertinent information. Also, within 24 hours, complete the eCRF with all available AE, demographic, medical history, concomitant medication, and study drug administration information. As additional information on a previously reported pregnancy becomes available, a follow-up Pregnancy Report Form should be prepared with the new information and submitted to the safety contact.

Subjects who become pregnant during the study will not receive any additional study drug and will be withdrawn from the study. The Investigator must strongly encourage these subjects to return to the study site for the final protocol-specified visit and assessments. In addition, the Investigator will monitor the pregnancies of subjects exposed to study drug or the partner of a male subject who may become pregnant while that subject is on study until final resolution (delivery, miscarriage, or early termination). Follow-up should occur monthly and should be documented in the study file. A follow-up Pregnancy Report Form must be completed for each follow-up contact with the subject or the partner of a male subject who became pregnant while that subject is on study and submitted to the Sponsor's designated safety contact. Report a spontaneous miscarriage, therapeutic abortion, stillbirth, or congenital anomaly as an SAE (Section 10.3).

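### Protocol 8.3.1.2 takes subjects with severe or recurrent hypersensitivity off the study rather than off treatment, which read literally ends the survival follow-up that other sections keep

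*Protocol*

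**What the plan says.** Protocol 8.3.1.2 has two instructions. A subject with anaphylaxis or a Grade 3 or higher "hypersensitivity reaction/infusion reaction should be discontinued from the study". For milder reactions that are re-challenged: "If the hypersensitivity reactions are experienced at the re-challenge, the subject should be discontinued from the study".

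The protocol separates leaving treatment (7.3.1) from leaving the study (7.3.2), and 7.3.2 attaches a consequence to the second: "Long-term follow-up will continue until the subject discontinues from the study".

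For subjects who stop both drugs, the follow-up rule is stated several times:

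- Protocol 6.1.3: such subjects "will be followed every 12 weeks for survival until death, withdrawal of consent, or lost to follow-up". Protocol 6.1.4 and SAP 3.5 give the same rule.
- Protocol 7.3.1: "Subjects who discontinue treatment with PEGPH20 and pembrolizumab should enter long-term follow-up unless they withdraw consent, die, or are lost to follow-up".
- Protocol 8.1.2.4: "After the End of Treatment Visit, all subjects will enter long-term follow-up". Survival status and subsequent anti-cancer therapies are then collected every 12 weeks.

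Under SAP 4.7.1, OS for surviving subjects is censored at the last contact.

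**The concern.** In this protocol, leaving the study and leaving treatment are different events with different consequences. Section 8.3.1.2 is the text a site opens when a reaction happens, and it names the event that closes follow-up. A site that complies exactly would make no further 12-weekly contacts, and the subject's OS would be censored at about the time of the reaction. Because the cause is a reaction to a study drug, the censoring might be related to prognosis, and the cohorts are small: SAP 4.7.2 reports 17 NSCLC and 25 gastric subjects enrolled in Dose Expansion. At stake are later deaths and later therapies for the few subjects who meet the rule.

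**Working it through.** The plan states no figure on this point, so the check is mainly a comparison of sections.

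**1. What triggers exit.** In 8.3.1.2: anaphylaxis, a Grade 3 or higher hypersensitivity or infusion reaction, or a reaction at re-challenge. The action in each case is discontinuation from the study.

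**2. What exit does.** Under 7.3.2, long-term follow-up runs until the subject leaves the study. Steps 1 and 2 together end survival follow-up at the reaction.

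**3. What the follow-up sections allow.** Sections 6.1.3, 6.1.4, 7.3.1 and 8.1.2.4 and SAP 3.5 name three exits: death, withdrawn consent and loss to follow-up. None makes an exception for hypersensitivity.

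**4. Where an adverse event belongs.** Section 7.3.1 lists an adverse event as a reason to stop treatment. Section 7.3.2 lists death, withdrawn consent, loss to follow-up, sponsor termination and an open category for other reasons; it does not name an adverse event. The structure therefore places hypersensitivity under 7.3.1, with follow-up continuing. Section 8.3.1.2 as worded places it under 7.3.2. The two cannot both be followed.

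**5. Which endpoints depend on it.**
- ORR: long-term follow-up schedules no scans, so losing it removes no response assessment.
- Progression-free survival (PFS): SAP 4.7.1 does not count a death more than 7 days after the last dose without progression, so the later deaths that would be missed are not PFS events in any case.
- OS: affected, by censoring at last contact.

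**6. Size per affected subject, as an illustration only.** Take n subjects, let one be censored before any other event, and assume no other censoring before month 12. The 12-month Kaplan-Meier estimate then equals the survival S of the other n − 1. Compared with full follow-up, it is too high by S/n if that subject died before month 12, or too low by (1 − S)/n if alive.

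- NSCLC: n = 17; S = 0.50, assumed from the 12.0-month median OS in Protocol 4.6.1. Shift: 0.50/17 = 2.9 points up or 2.9 points down. 80% half-width: 1.2816 × √(0.50 × 0.50/17) = 15.5 points.
- Gastric: n = 25; S = 0.69² = 0.476, assumed from the 6-month rate of 69% in Protocol 4.6.2 carried to 12 months at a constant hazard. Shift: 0.476/25 = 1.9 points up or 0.524/25 = 2.1 points down. 80% half-width: 1.2816 × √(0.476 × 0.524/25) = 12.8 points.
- Assumed medians of 8 to 16 months with exponential survival (S = 0.354 to 0.595): 1.4 to 3.8 points in either direction across the two cohorts, against half-widths of 12.3 to 15.5 points.

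If the censoring is unrelated to prognosis, the expected shift is zero. The survival inputs come from pembrolizumab-alone populations not selected as HA-high, and the gastric one was PD-L1 positive. SAP 4.7 also analyses OS with both portions pooled, where one subject weighs less.

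**7. What cannot be computed.** The total effect needs the number of subjects meeting the rule and the relation between reactions and survival. The documents give neither.

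**The case against.** The best reply is that this is loose wording and the protocol already answers the question. Sections 6.1.4, 7.3.1, 7.3.2 and 8.1.2.4 all send a subject who stops study treatment into long-term follow-up. The protocol uses similar wording elsewhere where only the end of treatment can be meant. Table 2 footnote f, 8.1.2.2.5 and 8.2.15 speak of progression this way ("For subjects who are withdrawn from the study due to clinical disease progression"), while 6.1.4 treats clinical progression as a reason to stop treatment, with survival follow-up after. Section 10.7 says pregnant subjects "will be withdrawn from the study" and then requires monthly follow-up of the pregnancy. Section 8.3.1.2 also requires immediate contact with the sponsor at any hypersensitivity reaction, so each case offers an occasion to clarify. Early deaths would largely be recorded anyway through the 30-day adverse event window (10.2), the recording of deaths from progression (10.4.2), open-ended reporting of related serious events (10.5) and the broad last-contact rule in SAP 4.7.1.

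Most of this stands, and it limits the point to a minor one. It does not remove it. The general sections show what was probably intended, but the specific instruction says otherwise. The open category in 7.3.2 could record such an exit but would not reconcile it with sections that allow only three exits. The protocol is exact for thromboembolic events, where 7.3.1 stops PEGPH20 and lets pembrolizumab continue, so the same precision is available here.

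A reader might infer that the pregnancy and clinical-progression wording is the same error. The documents do not support that: in both cases the surrounding text shows that contact continues, and no result changes.

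**Conclusion.** The conflict holds, at minor severity. Section 8.3.1.2 read with 7.3.2 ends survival follow-up after a severe or recurrent hypersensitivity reaction, and five other places keep it. If sites follow the letter, OS for those subjects is censored at last contact because of a drug reaction, and mainly later deaths and subsequent therapies are lost. OS is secondary and carries no hypothesis test; the primary ORR test is unaffected.

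A reader might go further and infer that the plan does drop these subjects from survival follow-up, or that reported OS will be overstated. Neither is supported. The protocol as a whole favours continued follow-up, nothing shows how sites acted, and the documents contain no hypersensitivity rate and no link between such reactions and survival. Any upward bias would rest on an assumed excess hazard. The per-subject shifts above show only that one affected subject moves the 12-month estimate by far less than its 80% half-width.

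**What to change.** In both sentences of 8.3.1.2, replace *from the study* with *from study treatment*. The sponsor should confirm whether both drugs stop or only PEGPH20, since elsewhere the protocol uses study treatment for the two together. Add one sentence: 12-weekly follow-up for survival and subsequent therapy continues under 7.3.1 and 8.1.2.4 unless consent is withdrawn.

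For consistency, the similar phrases in 10.7, Table 2 footnote f, 8.1.2.2.5 and 8.2.15 may be aligned; this is optional.

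The cost is wording only: the 12-weekly contacts already exist, so no visits or data items are added. SAP 4.7.2 records that enrollment stopped on 31 May 2018, so a short clarification to sites would do for subjects still in follow-up. A check of recorded study-exit reasons would show whether anyone was affected.

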8.3.1.3. PEGPH20 Dose Modification Guidelines

PEGPH20 dose adjustments are allowed based on toxicities that are deemed related, possibly related, or probably related to PEGPH20. See Table 6 for guidelines.

Table 6: PEGPH20 Dose Adjustment and Toxicity Management Guidelines

Event	Management/Action
Musculoskeletal	
Any Grade 1 MSEs	• No change in PEGPH20 dose or frequency. Prescribed medication such as narcotics, muscle relaxants and other analgesics (with the exceptions of steroids), OTC drugs and physical therapy can be used at the Investigator's discretion.
Any Grade 2 MSEs	Based on Investigator's discretion use prescribed medication such as narcotics, muscle relaxants and other analgesics (with the exceptions of steroids), OTC drugs and physical therapy.
	• If the MSEs resolve or decrease to Grade 1 with administration of prescribed medication such as narcotics, muscle relaxants and other analgesics (with the exceptions of steroids), OTC drugs and physical therapy, PEGPH20 can be continued.
	• If the MSEs persist at Grade 2 despite administration of prescribed medication such as narcotics, muscle relaxants and other analgesics (with the exceptions of steroids), OTC drugs and physical therapy, the Investigator must discuss any further PEGPH20 treatment with the Sponsor's Medical Monitor.
Any Grade 3 or 4 MSEs	Hold PEGPH20 treatment.
	Based on Investigator's discretion use prescribed medication such as narcotics, muscle relaxants and other analgesics (with the exceptions of steroids), OTC drugs and physical therapy.
	• If the MSEs decrease to ≤ Grade 2, the Investigator must discuss any PEGPH20 treatment reinitiation with the Sponsor's Medical Monitor.
	• If the MSEs persist at Grade 3 or 4 levels, PEGPH20 should not be resumed.

Table 6: PEGPH20 Dose Adjustment and Toxicity Management Guidelines (Continued)

Event	Management/Action		
All non-MSE Events (Except TE Even	ts) Potentially Related to PEGPH20		
Grade 1 or 2	No change in PEGPH20 treatment.		
Grade 3	• Hold PEGPH20 treatment.		
	• If toxicity is resolved to baseline within 14 days, treatment may resume at the same dose level.		
	• If toxicity is reduced to ≤ Grade 2 within 14 days, treatment may resume but at next lower dose but must be discussed and decided upon mutual agreement with the Sponsor's Medical Monitor.		
	• If toxicity persists at Grade 3, any consideration to resume PEGPH20 treatment must be discussed with the Sponsor's Medical Monitor.		
Grade 4	Hold PEGPH20 treatment.		
	• If toxicity is resolved or reduced to ≤ Grade 2, any PEGPH20 treatment reinitiation must be discussed with the Sponsor's Medical Monitor.		
Thromboembolic Events (Regardless of	ess of Relatedness to PEGPH20)		
Any Grade TE event	Discontinue PEGPH20 treatment for subjects who experience any TE requiring full dose anticoagulation while on study. Treatment with pembrolizumab may continue as deemed appropriate by the Investigator.		

Abbreviations: MSE = musculoskeletal event; NSAIDs = non-steroidal anti-inflammatory drugs; PEGPH20 = PEGylated recombinant human hyaluronidase.

If PEGPH20 is held on Day 1 of treatment cycles 2+, pembrolizumab must still be given.

For details on administration of piroxicam and toradol for the management of MSEs, refer to Section 10.12.1; for information on administration of prophylactic enoxaparin and aspirin for management of TE events, refer to Section 10.12.2 and Section 10.12.3, respectively.

8.3.2. Pembrolizumab

8.3.2.1. Pembrolizumab Administration

Pembrolizumab will be administered by IV infusion at a dose of 2 mg/kg (in Dose Escalation) or 200 mg (in Dose Expansion) over 30 minutes once every 21 days on Day 1 of each cycle, 4-6 hours after the PEGPH20 dose.

The pembrolizumab dose will be individually calculated for all infusion visits in Dose Escalation according to the subject's screening weight. In calculating the dose, there will be no downward

adjustment to "ideal" body weight unless institution policy requires it. Doses should be readjusted if the subject's weight changes by >10%. If the subject's weight changes by $\le 10\%$, no adjustment is necessary unless the site has a standard procedure to adjust doses based upon current weight.

All Cycle Day 1 administrations of pembrolizumab should occur 4-6 hours after PEGPH20 administration.

8.3.2.2. Identified Risks of Pembrolizumab Treatment

Refer to the current Keytruda[®] US Prescribing Information for the identified risks associated with pembrolizumab treatment.

8.3.2.3. Pembrolizumab Dose Adjustment and Toxicity Management

Dose adjustments (reduction, interruption, and discontinuation) and toxicity management should be undertaken per the current Keytruda® US Prescribing Information.

8.4. Excluded Concomitant Medications and Study Restrictions

Concurrent chronic use of IV heparin is prohibited; however, for acute TEs, IV heparin may be used. PEGPH20 administration must be stopped during this period. Use of megestrol acetate is prohibited.

Any other anti-cancer agents or investigational agents are prohibited while the subject is on study. After treatment is discontinued and a subject enters long-term follow-up, the subject will not have any restrictions (i.e., when being followed every 12 weeks to collect survival and anti-cancer therapy data).

The use of systemic corticosteroids or immunosuppressants before starting pembrolizumab should be avoided because of their potential interference with the pharmacodynamic activity and efficacy of pembrolizumab. However, systemic corticosteroids or other immunosuppressants can be used after starting pembrolizumab to treat immune-related adverse reactions (see Section 8.3.2.2).

